2.2.2 Secondary

• To observe clinically relevant responses to therapy (defined in section 11.2) as determined by bone marrow biopsy after cycle 1

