4.1.2 Exclusion Criteria

An individual who meets any of the following criteria will be excluded from participation in this study:

1. Patients must not have evidence of active CNS disease

2. Patients must not be receiving any chemotherapy agents (except hydroxyurea). Intrathecal methotrexate and intrathecal cytarabine are permissible.

3. Patients must not be receiving growth factors (G-CSF, GM-CSF), except for erythropoietin.

4. Patient must not have a concurrent active malignancy for which they are receiving treatment..

5. Patients with other severe concurrent disease which in the judgment of the investigator would make the patient inappropriate for entry into this study are ineligible.

6. Patients must not have received any investigational agents within 30 days of study entry unless they have exceeded 5 terminal half-lives of the previous study drug used for treatment.7. Patients must not be pregnant or breastfeeding. Pregnancy tests must be obtained for all females of child-bearing potential within 10 days prior to enrollment. Pregnant or lactating patients are ineligible for this study due to the potential human fetal or teratogenic toxicities of palbociclib. Males or women of childbearing potential may not participate unless they have agreed to use an effective contraceptive method (defined as hormonal contraceptives, intrauterine devices, surgical contraceptives, or condoms).

8. Patients who have uncontrolled infection are not eligible. Patients must have any active infections under control. Fungal disease must have been adequately treated for at least 2 weeks before study entry. Subjects with bacteremia must have documented negative blood cultures prior to study entry.

9. Patients who are candidates for allogeneic transplantation, have a suitable donor, and are willing to undergo transplantation.

10. Patients who are eligible for and willing to receive treatment with tisagenlecleucel.

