** Optimal therapy for vomiting and diarrhea should be based on institutional guidelines with consideration of the prohibited medications listed in these protocol guidelines.

The design is constructed to reduce the chance of escalating the dose when the probability of DLT is high, and increase the chance of escalating the dose when the probability of DLT is low. The maximum tolerated dose (MTD) is defined as the highest dose level where a DLT occurs in at most one out of six patients treated. The escalation scheme is as follows:

(1) If none of the initial three patients in a cohort experiences a DLT, then a new cohort of three patients will be treated at the next higher dose level.

(2) If one of the three patients in a cohort experiences a DLT, then up to three additional patients will be treated at the same dose. Escalation will continue if only one of six patients experiences DLT.

(3) If two or more patients in a cohort experience DLT, then the MTD will have been exceeded, and no further dose escalation will occur. The previous dose level will be considered the MTD.

(4) If only three patients were treated at a dose level under consideration as the MTD, then up to three additional patients will be accrued. If no more than one of the six patients at that dose level experience a DLT, then that dose level will be confirmed as the MTD. If two or more patients in that cohort experience DLT, then the previous dose level will be studied in the same fashion.

The MTD is defined as the highest dose studied for which the observed incidence of DLT is less than 33%. Frequencies of toxicities will be tabulated according to the NCI Common Toxicity Criteria. Patients will be continued to be followed for one year for evidence of late toxicity.

Table 1.1 below gives the probabilities of dose escalation based on true DLT risk in the 3+3 design.

True DLT rate										
		10%	20%	30%	40%	50%	60%	70%	80%	90%
Probability c escalation	of	0.91	0.71	0.49	0.31	0.17	0.08	0.03	0.01	0.001

All patients treated with at least one dose will be included in the safety analysis.

Response criteria for the study are defined as follows:

Response Criteria Complete Remission (CR) No lymphoblasts in the bone marrow Absolute neutrophil count ≥0.75 x10⁹/L Platelet count ≥75 x 10⁹ /L

Complete Remission with Incomplete Hematologic Recovery (CRi)

<5% lymphoblasts in the bone marrow

Partial Remission (PR)

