All criteria for CR are satisfied except there are between 5% and 25% lymphoblasts in the bone marrow

Stable Disease (SD)

Failure to achieve at least a PR, but with no evidence of progression as defined as an increase of peripheral blood or bone marrow blasts of more than 10% from nadir during study.

Progressive Disease (PD)

For patients with < 5% blasts at baseline, there must be an increase to \ge 10% blasts. For patients with 5% to 10% blasts at baseline, there must be a \ge 50% increase to > 10% blasts.

For patients with 10% to 20% blasts at baseline, there must be a \ge 50% increase to \ge 20% blasts.

Response rate defined as the proportion of patients who achieve a CR, CRi, PR, or SD response will be estimated along with a 95% confidence interval.

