Appendix A: Schedule of Events

Appendix B: ECOG Performance Status

Appendix C: Sample Handling, Processing, and Storage Instructions

Appendix D: Requesting a Dose Escalation/Expansion Approval

APPENDIX A: SCHEDULE OF EVENTS

	Baseline	Induction Day+1	Induction Day +4 ¹⁰	Induction Day +8	Induction Day +12 ¹⁰	Induction Days +14 and +21 ¹⁰	Induction Day +28 ¹⁰	Maintenance Cycle 1 (weekly)	Maintenance Day +28 ¹⁰ *	Maintenance Cycles 2-6 (every other week) ¹¹	Follow-up ^{7,8}
Informed Consent	X1										
Medical/Oncologic History	X1										х
Physical Examination (including neurological exam)	X ¹	x		x			x		X		
Vital Signs	X1	X		Х			X		х		
Performance Status	X1										
Review of concomitant medications	X1	x		x			x		x		x
Adverse Event Assessment		х		х			х		х		X ⁶
Laboratory Studies											
CBC with differential	X1	х	х	х	х	x	х	x	х	x	
Serum Chemistry, Electrolytes	X ^{1,7}	X ⁷	х	X ⁷	x	x	X ⁷	x	X ⁷	x	
Liver Function Tests	X1	х	х	х	х	x	х	x	x	x	
Pregnancy test	X ^{1,2}										
Pharmacokinetics		X ³		X ³							
Pharmacodynamics	X ³	X ³		X ³							
Tests & Studies											
Bone Marrow Biopsy/Aspirate ⁹	X ^{1,4}						x		x		X ⁵
Investigational Agent											
Pill Diary Given to Patient	X1										

Note: Palbociclib will be given with a one week lead-in starting on Day -7 to Day -1. *Patients who continue treatment for multiple cycles will have the maintenance Day +28 procedures repeated for each cycle.

- To be done within twenty-one days prior to first dose of study drug unless otherwise indicated (with exception to the bone marrow biopsy/aspirate which is required at any time prior to study treatment). Informed consent, baseline procedures, and confirmed eligibility must be completed prior to the one week lead in with Palbociclib (starting on Day -7)
- 2. Only perform for females of child bearing potential (serum or urine)
- 3. Blood to be drawn prior to administration of palbociclib and dexamethasone on day +1, and day +8. PK samples will be one tube of 3-4mL. PD samples are 10mL each.
- 4. The bone marrow aspirate may be replaced by 20 mLs of peripheral blood if the patient has a peripheral leukemic blast count ≥200/μl.
- 5. In patients who attain a CR, a bone marrow should ONLY be performed after cycle 1 maintenance if there is a suspicion/evidence of relapse based on peripheral blood studies or other clinical indications during the follow up period.

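### CR, CRi and PR in Section 11.2 carry no condition on circulating blasts or extramedullary/CNS leukemia, isolated new extramedullary/CNS disease meets no PD rule, and the PD and SD wording can conflict with CR

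*Combined protocol and SAP*

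**What the plan says.** Section 2.2.2 makes clinical response the secondary endpoint, "as determined by bone marrow biopsy after cycle 1", and refers to Section 11.2 for the definitions. Section 11.2 gives:

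- **CR:** "No lymphoblasts in the bone marrow", with "Absolute neutrophil count ≥0.75 x10⁹/L" and platelets of at least 75 x 10⁹/L.
- **CRi:** "<5% lymphoblasts in the bone marrow", and nothing further.
- **PR:** "All criteria for CR are satisfied except there are between 5% and 25% lymphoblasts in the bone marrow".
- **SD:** less than a PR, without progression. Progression is described here as a rise of more than 10% from nadir in blasts of either the blood or the marrow.
- **PD:** three bands by baseline blast percentage. The lowest begins "For patients with < 5% blasts at baseline, there must be an increase to" at least 10% blasts; the highest covers baselines of 10% to 20%. No band says whether marrow or blood is meant.
- **Response rate:** the proportion with CR, CRi, PR or SD, with a 95% confidence interval.

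Extramedullary or CNS leukemia appears in none of these. CNS disease appears as an entry exclusion in Section 4.1.2: "Patients must not have evidence of active CNS disease". The Appendix A row "Physical Examination (including neurological exam" is marked at baseline and at induction Day +28, as is the CBC with differential.

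**The concern.** A remission category that looks only at the marrow and the counts can be met while leukemia is present elsewhere. The situation is reachable under the entry rules: Section 4.1.2 excludes active CNS disease but no other extramedullary disease, Section 4.1.1 sets no minimum marrow blast percentage, and the PD bands themselves provide for baselines below 5%. As written, a patient whose relapse lies mainly outside the marrow could satisfy CRi on the baseline marrow.

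At stake are the CR and CRi counts within the only secondary endpoint and, for a patient who ought to be PD, the response rate itself. The categories are also used elsewhere. Section 3 lets CR, CRi, PR and SD go on to maintenance. Section 3.2 ties leaving the study for transplant to CR, and re-consent after 6 cycles to stable disease without CR.

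**Working it through.** The plan states no figure on this point to reproduce. The check applies the Section 11.2 definitions to constructed patients and then sizes the effect.

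**Step 1: classification.** Take a patient with 0% marrow lymphoblasts, neutrophils 1.0 and platelets 100 (both x 10⁹/L). CR is met because 0% satisfies the marrow condition, 1.0 ≥ 0.75 and 100 ≥ 75. The CRi marrow limit is met too. Now vary the baseline blast percentage and the current blood blast percentage, with a blood nadir of 0. The SD clause's 10% is read as percentage points, and the same baseline figure is used for either compartment; both are assumptions.

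| Baseline blasts | Blood blasts now | CR met | PD if marrow only | PD if blood counts | Progression wording in SD clause |
|---|---|---|---|---|---|
| 4% or 8% | 2% or 8% | yes | no | no | no |
| 4% or 8% | 15% or 30% | yes | no | yes | yes |
| 15% | 2% or 8% | yes | no | no | no |
| 15% | 15% | yes | no | no | yes |
| 15% | 30% | yes | no | yes | yes |
| 60% | 2% or 8% | yes | no band | no band | no |
| 60% | 15% or 30% | yes | no band | no band | yes |

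For the 15% baseline, PD needs a 50% increase (15 x 1.5 = 22.5%) and at least 20%, so 15% fails and 30% passes.

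Three results follow:

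1. CR is met in every row, whatever the blood shows.
2. At 15% or 30% blood blasts the same patient meets CR and the SD clause's description of progression. Section 11.2 has no precedence rule.
3. Whether PD is met depends on the unstated compartment. Above a 20% baseline there is no band at all.

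**Step 2: disease outside marrow and blood.** Keep the marrow and blood clear and add new CNS or other extramedullary leukemia. CR is still met. No PD band and no part of the SD clause is triggered under any reading, because each refers only to blasts.

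**Step 3: size.** Section 11.3 anticipates 12 to 18 patients. (Its stated maximum of 24 differs from the 18 in Section 3.1, so the anticipated range is used.) One patient changes a proportion by 1/N:

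- N = 18: 1/18 = 5.6 points
- N = 12: 1/12 = 8.3 points

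This is the change in the CR/CRi rate. The effect on the planned response rate depends on where the patient moves:

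- **CR or CRi to SD:** no change, because SD counts as response.
- **CR or CRi to PD:** one responder fewer. With assumed counts and exact (Clopper-Pearson) 95% intervals:
  - 6/18 = 33.3% (13.3 to 59.0) becomes 5/18 = 27.8% (9.7 to 53.5).
  - 4/12 = 33.3% (9.9 to 65.1) becomes 3/12 = 25.0% (5.5 to 57.2).

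**The case against.** The strongest reply is that circulating blasts are not ignored. The SD definition names them, and PD speaks of blasts without limiting them to the marrow. This stands against one tempting inference, that the criteria consist of marrow blasts and counts only and that a patient with circulating blasts can never be PD. The table shows otherwise at 15% and 30% blood blasts. It does not rescue CR, CRi or PR. The SD clause formally applies only to patients who fall short of PR, and the patient in question has already met CR.

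Second, a reader might infer that every misclassified patient inflates the response rate and is wrongly kept on treatment. The documents do not support that. SD is counted as response and SD patients also go to maintenance, so a correction from CR to SD changes neither. In addition, Section 4.4.1 lets the investigator end participation when an exclusion criterion arises during the study, which would reach new active CNS disease. Footnote 5 of Appendix A lets blood or clinical findings prompt another marrow in patients with CR. These are real safeguards, but the first is discretionary and neither assigns a response category.

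Third, Section 1.4.2 might be taken to mean that the analysis relies on CR as a stand-in for survival. It is a conditional statement about possible benefit, not an analysis rule.

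Finally, the stakes are limited: Section 11.1 tests no hypotheses, and response is a descriptive secondary estimate. That bears on priority, not on whether the definitions work.

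**Conclusion.** The point holds for the definitions. CR, CRi and PR can be assigned while leukemia is present in the blood or at an extramedullary or CNS site. Isolated new extramedullary or CNS leukemia meets no PD criterion. PD and the SD clause describe progression differently, and the SD wording can be met together with CR.

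The size is 5.6 to 8.3 points on the CR/CRi rate per misclassified patient, and the same on the response rate only for a patient who becomes PD. The only response estimate for which Section 11.2 specifies an interval is the combined rate including SD, so much of the effect falls on the breakdown by category.

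This rests on a denominator of 12 to 18 and on illustrative response counts. The documents give no frequency of extramedullary disease, so the expected number of affected patients cannot be stated. DLT, MTD and dose escalation are unaffected. The definitions should be corrected before response is assessed, but this does not threaten the primary objective.

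**What to change.** For the response endpoint in Section 11.2:

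1. Add to CR, CRi and PR that there are no circulating lymphoblasts and no known extramedullary or CNS disease, judged from the physical and neurological examination and the CBC with differential.
2. Record known extramedullary sites at baseline.
3. Name the compartment or compartments to which PD applies, reconcile PD with the progression wording in the SD definition, and state which category takes precedence when two are met.
4. State how new extramedullary or CNS disease is classified for the endpoint.

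Because Section 3 ends maintenance at disease progression, any change to PD may also affect continuation of treatment. The sponsor should reconcile that separately across Sections 3, 3.2, 4.4.1 and 11.2; no treatment rule is proposed here.

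The cost is protocol and CRF wording. The examinations and blood counts are already scheduled at baseline and Day +28, so no visit or test is added. The reported CR/CRi rate may be slightly lower.

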11.3 Sample Size Considerations

This traditional 3+3 dose escalation study will include a minimum of 4 and a maximum of 24 participants. The minimum sample size of 4 would be achieved if \geq 2 patients out of the first 3 patients have a DLT at dose levels 1 and -1. The maximum sample size of 18 would be achieved if 6 patients are enrolled at dose levels -1 through 3 (100 mg, 125mg, 150mg, 175mg). The anticipated sample size is 12-18.

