3.1 Number of Participants

A minimum of 4 and a maximum of 18 patients will be enrolled.

3.2 **Duration of Therapy**

Initially, patients will receive single agent palbociclib during induction for

pharmacokinetic/pharmacodynamics (PK/PD) evaluation followed by combination induction therapy with palbociclib and dexamethasone. Patients who do not achieve a CR, CRi, PR, or SD after induction therapy will be taken off the study. Patients who achieve a CR, CRi, PR, or SD will receive on palbociclib and dexamethasone maintenance until disease progression or dose limiting toxicity. Patients who are transplant ineligible at study entry but achieve a CR and thus become transplant eligible may come off study and proceed to transplant. Patients who achieve stable disease, but not a CR, will be re-consented after 6 cycles to continue on the study.

3.3 **Duration of Follow Up**

Patients will be followed for late toxicities for 1 year following the discontinuation of therapy.

3.4 **Study Timeline**

3.4.1 **Primary Completion**

We anticipate that accrual will be complete within 42 months.

3.4.2 **Study Completion**

The study will be complete 2 years after the enrollment of the last patient (66 months total study duration).

4 Study Enrollment and Withdrawal

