	 Grade 3 indirect hyperbilirubinemia that resolves to < grade 2 within 72 hours 								
Renal	Any ≥ Grade 3 toxicity								
Non-	≥ Grade 3, including electrolyte abnormalities, except as noted elsewhere in								
Hematologic	the table								
Exceptions to	Grade 3 alopecia								
DLI criteria	Grade 3 fatigue of < 5 days' duration								
	Grade 3 electrolyte abnormalities that last <72 hours								
	 Infection (including neutropenic fever), unless the investigator 								
	determines that the infection or neutropenic fever resulted from the degree or duration of myelosuppression in the absence of persistent								
	ieureillia								

* CTCAE version 5.0 should be used for grading.

** Optimal therapy for vomiting and diarrhea should be based on institutional guidelines with consideration of the prohibited medications listed in these protocol guidelines.

The DLT evaluation period is defined as 35 days (one week lead-in plus Cycle 1). In order to be considered evaluable, the patient needs to take 80% of the doses in the one week lead-in and Cycle 1 (1 cycle=28 days). The 80% completion can be non-consecutive days of dosing with study drug within the one week lead-in and Cycle 1. Any DLT will be followed until resolution.

If one DLT is recorded, then three additional patients will be enrolled into the present cohort. If no further DLTs occur (1 out of 6 DLTs) then the next patient will be enrolled in the next higher cohort. If 2 out of 6 patients have an observed DLT in any given cohort, 3 additional patients will be treated at one dose level lower, and if no additional DLTs are observed, this will be the maximum tolerated dose. If no DLTs are observed in all three cohorts then the expansion phase dose will be cohort 3 for the expansion phase. Toxicities will be graded according to the National Cancer Institute, Common Toxicity Criteria for Adverse Events version 4.0 (NCI CTCAE v5.0). If multiple toxicities are seen, the presence of DLT will be based on the most severe toxicity experience.

Once three patients have enrolled onto the dose cohort and the DLT evaluation period or the third patient has passed, a meeting will be held with the PI and the TJU Medical Monitor to review the safety information. If it is determined safe to open the next dose cohort, a formal letter from the Medical Monitor will be issued. Please see Appendix D for more information.

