11.2 Analysis Plans

This aim will consist of a Phase I trial of palbociclib to determine the maximum tolerated dose (MTD) of palbociclib when given in combination with dexamethasone. A standard 3+3 dose escalation design will be employed: three dose levels of palbociclib will be explored (100mg, 125mg, 150mg). Patients will be treated in cohorts of size three to six and the dosage will be escalated if the clinical toxicity is acceptable.

Patients who experience a DLT during the evaluation period as defined in section 6.2.1 will stop the study drugs and come off of the trial.

Patients who complete the first cycle of maintenance but require treatment to be held up to 4 weeks to achieve count recovery, will have palbociclib resumed with a level -1 dose reduction. A dose-limiting toxicity (DLT) is defined in the table below:

Toxicity	DLT Criteria*								
Hematology	 Marrow aplasia (defined as <10% cellularity with <10% blasts for ≥ 6 weeks not attributable to disease) 								
	• Grade 4 neutropenia persisting ≥6 weeks from the start of a cycle that								
	is not attributable to the underlying disease								
Cardiac	Any ≥ Grade 3 toxicity								
Gastro-intestinal	Any ≥ Grade 3 toxicity except:								
	 Grade 3 nausea, vomiting**, or diarrhea** not requiring total parenteral nutrition (TPN) or tube-feeding 								
Hepato-biliary	An increase in AST or ALT >3 x ULN and concurrent increase in total								
	bilirubin >2 x ULN (Hy's Law)								
	Any \geq Grade 3 toxicity except:								
	Any Grade 3 or 4 liver abnormalities (AST, ALT, or alkaline								
	phosphatase) that resolve to < grade 2 within 72 hours								
	 Grade 3 hyperbilirubinemia that resolves to < grade 2 within 72 hours One de 2 in dimensional that resolves to < grade 2 within 72 hours 								
	 Grade 3 indirect hyperbilirubinemia that resolves to < grade 2 within 72 hours 								
	nours								
Renal	Any ≥ Grade 3 toxicity								
Non-	≥ Grade 3, except as noted elsewhere in the table								
Hematologic									
Exceptions to	Grade 3 alopecia								
DLT criteria	 Grade 3 fatigue of < 5 days' duration 								
	 Grade 3 electrolyte abnormalities that last <72 hours 								
	 Infection, unless the investigator determines that the infection resulted 								
	from the degree or duration of myelosuppression in the absence of persistent leukemia								

* CTCAE version 5.0 should be used for grading.

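### The maximum sample size is given as both 18 and 24, the stated basis for 18 works out to 24, and the doses listed with it contradict the dose tables

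*Combined protocol and SAP*

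**What the plan says.** Protocol section 3.1 sets the limit: "A minimum of 4 and a maximum of 18 patients will be enrolled".

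Section 11.3 gives two maxima and an expected range:

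- First sentence: "This traditional 3+3 dose escalation study will include a minimum of 4 and a maximum of 24 participants".
- Third sentence: "The maximum sample size of 18 would be achieved if 6 patients are enrolled at dose levels -1 through 3 (100 mg, 125mg, 150mg, 175mg".
- Last sentence: "The anticipated sample size is 12-18".

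Section 11.2 describes the escalation: "three dose levels of palbociclib will be explored (100mg, 125mg, 150mg", and "Patients will be treated in cohorts of size three to six". Rule (4) of 11.2 sends the trial downwards when a candidate maximum tolerated dose (MTD) fails: "then the previous dose level will be studied in the same fashion". Section 6.2.1 words its own step-down differently, for two DLTs in six patients: "3 additional patients will be treated at one dose level lower, and if no additional DLTs are observed".

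The dose tables in 5.4 and 6.2.1 define levels -1, 1, 2 and 3 as 75, 100, 125 and 150 mg of palbociclib. Section 1.2 gives 150 mg as the highest dose, and 5.3 and 11.2 name nothing above it. Section 11.3.1 makes replacement of patients who are not DLT-evaluable mandatory.

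**The concern.** The maximum is the operative enrolment limit, and the protocol gives two values for it. At the nineteenth patient the site could not tell from the text whether it was still within protocol. The sentence meant to justify 18 does not justify it, and it pairs the named levels with doses that the tables do not assign to them: it omits 75 mg and includes 175 mg, a palbociclib dose found nowhere else in the document. The reader also cannot tell whether level -1 is inside the limit, or whether replaced patients count towards it.

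**Working it through.** **1. The plan's own figure.**

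- Stated basis: six patients at each of levels -1, 1, 2, 3. The tables have no level 0, and the sentence itself lists four doses. 4 x 6 = 24. This matches the first sentence of 11.3, not the 18 it is offered for.
- 18 is reproduced only as 3 x 6, using the three levels named in 11.2 and leaving out level -1, which the sentence expressly includes.

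**2. The dose list.**

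| Level | Tables in 5.4 and 6.2.1 | Sentence in 11.3 |
|---|---|---|
| -1 | 75 mg | 100 mg |
| 1 | 100 mg | 125 mg |
| 2 | 125 mg | 150 mg |
| 3 | 150 mg | 175 mg |

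**3. Ceiling under 11.2 rules (1)-(4).** All paths were enumerated in whole cohorts of three, starting at level 1, with at most six evaluable patients per level.

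- Without level -1: totals of 3 to 18.
- With level -1: totals of 6 to 24.
- A path to 24: 0/3 at level 1; 0/3 at level 2; at least 2/6 at level 3; level 2 expanded to six with at least two DLTs; level 1 expanded to six with at least two DLTs; six at level -1. That is 6 + 6 + 6 + 6 = 24.

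The stated minimum of 4 implies stopping within a cohort, so the lower ends do not match it. The upper ends are unaffected.

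**4. How often 18 is passed.** The documents give no DLT rates and no non-evaluable rate, so both are assumed. Let N be the number of evaluable patients under 11.2 with level -1 available, and q the chance that a patient is non-evaluable, independent of everything else. Enrolment passes 18 when fewer than N of the first 18 patients are evaluable: P = P(Bin(18, 1 - q) < N).

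- N = 18: 1 - 0.9^18 = 0.850 for q = 10%; 1 - 0.8^18 = 0.982 for q = 20%.
- N = 15: 0.098 and 0.499.
- N = 12: 0.001 and 0.051.

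Worked case, DLT rates 5%, 10%, 20%, 30% at levels -1, 1, 2, 3: P(N = 12) = 0.491, P(N = 15) = 0.310, P(N = 18) = 0.078, P(N > 18) = 0.0006.

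- q = 10%: 0.491 x 0.001 + 0.310 x 0.098 + 0.078 x 0.850 + 0.0006 = 0.098.
- q = 20%: 0.491 x 0.051 + 0.310 x 0.499 + 0.078 x 0.982 + 0.0006 = 0.257.

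| Assumed DLT rates, levels -1, 1, 2, 3 | P(N > 18 evaluable) | P(enrolled > 18), q = 10% | P(enrolled > 18), q = 20% |
|---|---|---|---|
| 10% at all | 0.005% | 7% | 22% |
| 20% at all | 0.09% | 9% | 22% |
| 30% at all | 0.29% | 7% | 15% |
| 40% at all | 0.37% | 4% | 9% |
| 5, 10, 15, 20% | 0.03% | 9% | 25% |
| 5, 10, 20, 30% | 0.06% | 10% | 26% |
| 10, 20, 30, 40% | 0.30% | 9% | 19% |
| 20, 30, 40, 50% | 0.47% | 6% | 13% |

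**5. The 6.2.1 wording.** It adds three patients one level lower and makes no exception for a level that already has six. Read literally, 1/6 at level 1, 1/6 at level 2 and 2/6 at level 3, then three more at level 2, gives 6 + 6 + 6 + 3 = 21 without opening level -1. With assumed DLT rates of 20%, 30% and 40% at levels 1 to 3, and reading the trigger as at least two DLTs, the path has probability:

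- level 1, one DLT then none: 3(0.2)(0.8^2) x 0.8^3 = 0.197;
- level 2, the same: 3(0.3)(0.7^2) x 0.7^3 = 0.151;
- level 3, one DLT then at least one: 3(0.4)(0.6^2) x (1 - 0.6^3) = 0.339;
- product: 0.197 x 0.151 x 0.339 = 0.010, about 1%.

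**The case against.** The strongest defence is that 18 is a sensible figure for the three levels that 11.2 says will be explored, that it is the top of the anticipated range, and that the 11.2 rules almost never take the trial past 18 evaluable patients. No hypothesis is tested (11.1), so neither power nor type I error depends on the maximum, and the correction is editorial.

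Most of this stands as description. It does not remove the conflict: the third sentence of 11.3 calls 18 the maximum, not the anticipated size, and counts level -1 in it.

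A reader might infer from the under-0.5% figure that the conflict has no practical effect. The documents do not support that, because the limit in 3.1 is on patients enrolled while the figure counts evaluable patients before replacement. A plain reading of 3.1 already includes replaced patients, so the silence on replacement is a point to clarify, not a separate error.

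A reader might also infer that 24 is the true maximum. It is the arithmetic of the 11.3 sentence and the ceiling under 11.2 with level -1, but it is not shown to hold under 6.2.1, whose step-down differs.

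Nor does the frequency with which level -1 opens (about 10% to 75% over the assumed profiles under 11.2) measure the harm. When it does open, N exceeds 18 at most 0.93% of the time, and the trigger for level -1 in 5.4 is worded differently from the one modelled.

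**Conclusion.** The stated maximum is wrong as written. It is 18 in 3.1, and 24 and then 18 in 11.3; the basis given for 18 yields 24, a difference of six patients. The dose list in the same sentence contradicts the dose tables and the 150 mg maximum.

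Under 11.2 in whole cohorts, the ceiling is 18 evaluable patients without level -1 and 24 with it, and more than 18 is rare (0.005% to 0.47%). For enrolment the conflict matters more: about 4-10% or 9-26% of trials would enrol more than 18 if 10% or 20% of patients were non-evaluable. These ranges rest on assumed DLT profiles, assumed and independent non-evaluability, and the 11.2 rules. The textual and arithmetic conflict rests on no assumption. It should be fixed, but it affects no planned analysis.

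**What to change.** 1. Reconcile the step-down wording of 6.2.1 with that of 11.2, including what happens at a level that already has six patients.
2. Reconcile the dose list in 11.3 with 1.2, 5.3, 5.4, 6.2.1 and 11.2. No view is given here on which doses or which clinical rule are right.
3. Then state one maximum, identical in 3.1 and 11.3, that matches the reconciled rule and the number of levels counted. If level -1 counts and the 11.2 rules are kept, that is 24 DLT-evaluable patients; under any other reconciled rule the ceiling has to be worked out again.
4. Say whether the maximum counts evaluable or enrolled patients, and whether those replaced under 11.3.1 are included.

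The cost is a restated figure, a sentence on replacements and a corrected dose list. The maximum may end up higher than the 18 in 3.1. The analysis does not change.
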